Research Proposal

Use of a “flash-free” adhesive resin for orthodontic bracket bonding: a clinical study of bonding time, bond survival, and adhesive remnant cleanup

[name], Dr med dent, PhD, [name], MS

Division of Orthodontics, Department of Developmental and Surgical Sciences, University of Minnesota

Background:

The time required for bracket bonding and cleanup of remnant adhesive from the enamel surface after bracket debonding are important determinants of the duration of the two longest appointments during orthodontic treatment. The development of “flash-free” adhesives resin for orthodontic bracket bonding, which is due on the market in the near future, now promises a decrease in chair time for both patient and orthodontist. However, questions remain regarding the bonding time and bond survival of orthodontic brackets bonded using these adhesives, and the time required for adhesive remnant cleanup. These factors will be critical in determining the acceptance of these new “flash-free” adhesive resins in the orthodontic community.

Purpose:

The purpose of this study is to compare (1) bonding time, (2) bond survival, (3) amount of adhesive remaining on the tooth surface after bracket debonding, and (4) time required for adhesive remnant cleanup between a new “flash-free” and a conventional adhesive resin for orthodontic bracket bonding.

Methods:

Thirty consecutive patients presenting for comprehensive orthodontic treatment with fixed appliances at the University of Minnesota, who are willing to participate, will be included in the initial study. Selection criteria will include full permanent dentition through the first molars, teeth with sound, non-carious buccal enamel and no pretreatment with chemical agents such as hydrogen peroxide, and no previous orthodontic treatment with fixed appliances. The patients will have their maxillary incisors, canines, and premolars bonded with ceramic orthodontic brackets pre-coated with a “flash-free” adhesive resin (Clarity Advanced Brackets “flash-free”, 3M Unitek Monrovia, CA, USA) on one side and a conventional adhesive resin (Clarity Advanced Brackets APC II, 3M Unitek) on the other side. The side allocation and order of bonding will be randomized for each patient.

A total of ten calibrated clinicians will perform the clinical procedures together with their dental assistants.

Bonding time

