The patient's teeth will be polished using a fluoride-free prophylaxis paste (Topex Prep&Polish, Sultan Healthcare, Hackensack, NJ, USA) on a rubber cup attached to a low speed handpiece, etched with 35% phosphoric acid (Temrex, Freeport, NY, USA) for 30 seconds, rinsed with water, air-dried, and primed using a conventional primer (Transbond Light Cure Adhesive Primer, 3M Unitek) following the manufacturer's instructions. The teeth will then be bonded according to the predetermined protocol with the "flash-free" product on one side (group 1) and the conventional (APC II) product on the other side (group 2) using a direct bonding technique. Excessive adhesive in group 2 will be removed with a sharp scaler. The adhesive will be light cured for 20 seconds (5 seconds on each side of the bracket) with a light-emitting diode polymerization device (Ortholux LED, 3M Unitek). The distance between the exit window and the adhesive surface will be maintained at less than 5 mm in order to obtain adequate polymerization. The time taken to bond each side will be timed to the nearest second using a digital stopwatch.

Bond survival

Possible bond failure will be recorded at standardized intervals of four weeks. In case of a bond failure, the patients will be asked about a possible explanation for the bond failure. Bond failure as a consequence of habits and trauma will be excluded from the evaluation.

Adhesive remnant cleanup

After completion of orthodontic treatment, the brackets will be debonded following the manufacturer's instructions. The order of debonding will be randomized for each patient. Once the brackets are debonded, the adhesive remnant index (ARI; Årtun and Bergland, 1984) will be scored under $\times 10$ magnification using an optical microscope (MVX10, Olympus, Tokyo, Japan).

Remaining adhesive will be removed from the tooth surfaces using a tungsten carbide finishing bur (H 283-21-012, Brasseler, Savannah, GA, USA) in a low speed handpiece until the enamel has regained its natural gloss (David *et al.*, 2002). Satisfactory removal of the remnant adhesive will be verified by visual inspection under a dental operating light. The time taken to clean up the residual adhesive in each quadrant will be timed to the nearest second using a digital stopwatch.

Statistical analysis

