Descriptive statistics will be applied to the data to obtain mean values and standard deviations, and the data will be tested for normality (Kolmogorov-Smirnov test). Differences between the groups will be tested for statistical significance using a Student's *t*-test if the data are normally distributed and a Mann-Whitney U test if the data are non-normally distributed. Bracket survival times will be compared using a Cox's *F* test. A Cochran-Armitage test will be used to determine if there is an association between group membership and ARI. For all tests, *P*-values of less than 0.05 will be considered statistically significant.

Approval:

Approval to conduct this study will be obtained from the Institutional Review Board at the University of Minnesota. Informed consent will be obtained from all participating patients. In case of minors, consent will be obtained from a parent or guardian; assent will be obtained from the minor.

Anticipated outcomes:

Following completion of this study it is expected that significant information will be gained regarding the following:

1. The time required for direct bracket bonding with a “flash-free” orthodontic adhesive resin compared to a conventional adhesive resin together with a possible decrease in chair time when using a “flash-free” product.
2. Bond survival of brackets bonded with a “flash-free” orthodontic adhesive resin compared to a conventional adhesive resin.
3. The amount of adhesive remaining on the tooth surface after bracket debonding using the above products.
4. The time required for adhesive remnant cleanup using the above products and possible decrease in chair time when using a “flash-free” product.
5. An independent assessment of the clinical performance, suitable for peer-reviewed publication, of a new “flash-free” orthodontic adhesive resin.

References:

Årtun J, Bergland S (1984). Clinical trials with crystal growth conditioning as an alternative to acid-etch enamel pretreatment. *Am J Orthod* 85:333–340.

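### Bonding and cleanup times are paired by the split-mouth design, but the planned tests are for independent groups; under positive correlation they are conservative and lose power

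*Combined protocol and SAP*

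**What the plan says.** The Methods section plans for "Thirty consecutive patients presenting for comprehensive orthodontic treatment with fixed appliances at the University of Minnesota". Each patient has one side of the upper arch bonded with each product, and "The side allocation and order of bonding will be randomized for each patient". The Bonding time section repeats the layout: flash-free "product on one side (group 1) and the conventional (APC II) product on the other side (group 2) using a direct bonding technique".

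Both timing outcomes are recorded within the patient. For bonding, "The time taken to bond each side will be timed to the nearest second using a digital stopwatch". For cleanup, "The time taken to clean up the residual adhesive in each quadrant will be timed to the nearest second using a digital stopwatch". Only upper teeth in front of the molars are bonded, so the two quadrants are the two sides.

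The Statistical analysis section gives the test in one sentence: "Differences between the groups will be tested for statistical significance using a Student's *t*-test if the data are normally distributed", and otherwise "a Mann-Whitney U test if the data are non-normally distributed". Normality is to be checked by Kolmogorov-Smirnov on the data, without saying whether that means the times or the differences. The document does not mention a paired t-test, a signed-rank test, a mixed model, or a patient or clinician effect.

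**The concern.** The two groups in the analysis are two sides of the same 30 mouths. A test for independent groups leaves the differences between patients in its error term. Removing those differences is the main statistical advantage of a split-mouth design. Differences between operators stay in as well: "A total of ten calibrated clinicians will perform the clinical procedures together with their dental assistants". The normality check has the same weakness if it is applied to the times, because a paired comparison depends on the distribution of the within-patient differences.

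Bonding time and cleanup time are two of the four stated purposes, and a possible saving in chair time is named under Anticipated outcomes for both. If the standard error is too large, a real saving may be reported as not significant. The document contains no sample-size calculation, so it shows no power margin that could absorb the loss.

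**Working it through.** **Which test is planned.** Student's t-test alone could mean the paired or the unpaired form. Its stated alternative, Mann-Whitney U, exists only for independent samples; the paired counterpart would be Wilcoxon signed-rank. The sentence is therefore most naturally read as unpaired in both branches. If the t-test were meant as paired, the two branches would contradict each other and the second would still be wrong.

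**Inputs from the document.** 30 patients, hence 30 pairs; significance level 0.05. There is no power, SD or target difference to reproduce.

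**Assumptions.** Two-sided test, normal data, equal SD σ on both sides, within-patient correlation ρ. The effect d is the mean difference divided by σ.

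**Standard errors.**
- True standard error of the mean difference: σ√(2(1−ρ)/30).
- Unpaired test uses: σ√(2/30).
- The unpaired standard error is therefore too large by the factor 1/√(1−ρ).

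**Effect on a p-value.** Take a paired result exactly at p = 0.05, so t = 2.045 on 29 df, with observed correlation ρ. The unpaired statistic is 2.045 × √(1−ρ) on 58 df:
- ρ = 0.3: 1.711, p ≈ 0.09
- ρ = 0.5: 1.446, p ≈ 0.15
- ρ = 0.7: 1.120, p ≈ 0.27

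**Effect on interval width,** if an interval is built from the unpaired test. The ratio of unpaired to paired width is [2.002 × √(2/30)] / [2.045 × √(2(1−ρ)/30)] = 0.979/√(1−ρ). This gives 1.17, 1.38, 1.79 and 2.19 at ρ = 0.3, 0.5, 0.7 and 0.8.

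**True type I error at nominal 5%,** simulated with 30 bivariate-normal pairs (40,000 runs for the t-test, 8,000 for Mann-Whitney):

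| ρ | Unpaired t | Mann-Whitney |
|---|---|---|
| 0 | 4.8% | 4.4% |
| 0.2 | 2.9% | 2.9% |
| 0.3 | 2.0% | 1.8% |
| 0.5 | 0.7% | 0.8% |
| 0.7 | 0.08% | 0.1% |

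The paired t-test and the signed-rank test stay near 5% throughout.

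**Power at a fixed effect,** unpaired t against paired t, same simulation:

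| ρ | d = 0.3 | d = 0.5 | d = 0.8 |
|---|---|---|---|
| 0 | 21% vs 20% | 48% vs 47% | 86% vs 85% |
| 0.3 | 17% vs 27% | 47% vs 61% | 90% vs 95% |
| 0.5 | 13% vs 36% | 47% vs 76% | 93% vs 99% |
| 0.7 | 8% vs 54% | 46% vs 93% | 97% vs 100% |

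At d = 0.5, Mann-Whitney against signed-rank gives 43% vs 73% (ρ = 0.5) and 44% vs 92% (ρ = 0.7).

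**Power when the effect is the one a paired t-test detects with 80% power.** That effect is 0.529 SD of the within-patient difference, so d = 0.529 × √(2(1−ρ)). This is 0.63, 0.53, 0.41 and 0.335 at ρ = 0.3, 0.5, 0.7 and 0.8. Against that 80%, the unpaired t-test has 69%, 53%, 25% and 9%. The effect in σ units shrinks as ρ rises here, so these figures must not be read as the loss for a fixed saving in seconds. The table above shows that loss.

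**The case against.** The strongest reply is that the error is on the safe side and its size is unknown. With positive correlation the unpaired tests reject too rarely, so a significant result would not be a spurious one. The document gives no correlation, SD or target saving. At ρ = 0 nothing is lost, and at d = 0.8 with ρ from 0.3 to 0.7 the loss is only 3 to 5 percentage points. A large bonding-time effect is plausible, because excess adhesive is scaled away only on the conventional side. The plan specifies no confidence interval, so the width ratios apply only if one is reported. Since the data are collected as pairs, the right analysis remains possible later.

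All of this stands as a limit on the size of the harm. It does not make the tests fit the design: they assume independence between two sides of one mouth, and the stated 0.05 level fails whenever ρ is not zero. A positive ρ is to be expected, since both sides share the patient. They probably share the clinician too, although the document does not say that one clinician treats both sides, so the removal of clinician variation by pairing is itself an assumption. Leaving the correction until after the results are seen would also turn the choice of test into a post hoc one.

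**Conclusion.** The concern holds and should be fixed before analysis. The design is paired, the named tests are not, and nothing elsewhere in the document corrects this. The direction is conservative under positive correlation: the harm is missed differences, not false claims. For ρ between 0.3 and 0.7, the unpaired t-test gives up about 14 to 46 points of power at d = 0.5 and about 10 to 45 points at d = 0.3, but little at d = 0.8. These sizes rest on assumed ρ and d, normal data, equal SDs and 30 complete pairs. The mismatch itself rests only on the text.

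**What to change.** Replace the t-test and Mann-Whitney sentence with:

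> Bonding time and cleanup time will be compared on within-patient differences (flash-free minus conventional) with a paired t-test. The mean difference in seconds and its 95% CI will be reported, with a Wilcoxon signed-rank test if the differences are clearly non-normal.

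Apply any normality check to the differences. State the criterion for switching tests, or report both tests, so that the choice is not left open. Base each analysis on the patients with both times: cleanup is timed only after treatment ends, so fewer than 30 pairs may remain.

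An optional refinement is a mixed model with patient and clinician as random effects and terms for side and order. This would address clustering of the differences within the ten clinicians and any order effect, but it is not needed to correct the error.

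The cost is one sentence of analysis wording, with no new patients, data or procedures.

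### Cox's F test treats up to 300 brackets as independent although they sit five per side in 30 split-mouth patients, so its p-value is not valid, and the plan reports no effect estimate

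*Combined protocol and SAP*

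**What the plan says.** The Methods section describes a split-mouth trial in "Thirty consecutive patients presenting for comprehensive orthodontic treatment with fixed appliances at the University of Minnesota". The teeth are the "maxillary incisors, canines, and premolars bonded with ceramic orthodontic brackets", with one adhesive on each side, and "The side allocation and order of bonding will be randomized for each patient". Procedures are shared among ten clinicians. Under Bond survival, "Possible bond failure will be recorded at standardized intervals of four weeks", and failures attributed to habits or trauma are left out.

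The whole survival analysis, in the Statistical analysis section, is: "Bracket survival times will be compared using a Cox's *F* test". That section mentions no pairing of sides, clustering of brackets, robust variance, frailty, hazard ratio or confidence interval. The only summaries it plans are means and standard deviations, which do not suit censored times.

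**The concern.** Cox's F refers a ratio of mean exponential scores to an F distribution with 2r1 and 2r2 degrees of freedom, where r1 and r2 are the failure counts in the two groups. Every failure is counted as independent information, and the two groups are taken as unrelated. The design breaks both conditions:

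- Both adhesives are tested in the same patients, who bring the same diet, oral care and clinician to each side.
- The five brackets of one adhesive in a patient share a side, and with it the chewing side, moisture control and place in the bonding order.

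These two kinds of sharing push the error rate in opposite directions, so the plan could declare a false difference or miss a real one, and the reader could not tell which risk applies.

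Bond survival is one of four stated purposes. The Background counts it, with bonding time and cleanup time, among the factors that will decide acceptance of the product. A bare p-value above 0.05 from few failures would leave open how much worse the new adhesive might be.

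**Working it through.** The plan gives no event count, power or failure rate, so there is no figure of its own to reproduce. The failure rates, correlations, frailty variances and treatment lengths below are assumptions. Tests are taken as two-sided at 0.05, because the plan does not state sidedness.

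**Bracket count.** Two incisors, one canine and two premolars give 2 + 1 + 2 = 5 per side. Then 5 × 30 = 150 per adhesive and 300 in all, in 60 sides and 30 patients. This is a maximum; it relies on the entry criterion of "full permanent dentition through the first molars".

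**Analytic check.** With m = 5 brackets per side, correlation ρw within a side and ρb between the two sides of a patient, the variance of the adhesive contrast, relative to independent brackets, is

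VF = 1 + (m − 1)ρw − mρb,

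and the true error rate of a nominal 5% test is 2 × [1 − Φ(1.96/√VF)].

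| ρw | ρb | VF | True error rate |
|---|---|---|---|
| 0.20 | 0.20 | 1 + 0.80 − 1.00 = 0.80 | 2.8% |
| 0.10 | 0.10 | 1 + 0.40 − 0.50 = 0.90 | 3.9% |
| 0.10 | 0.08 | 1 + 0.40 − 0.40 = 1.00 | 5.0% |
| 0.10 | 0.05 | 1 + 0.40 − 0.25 = 1.15 | 6.8% |
| 0.10 | 0 | 1 + 0.40 − 0 = 1.40 | 9.8% |

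The usual design effect, 1 + (m − 1)ρ, omits the last term and should not be used alone in a split-mouth trial.

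**Simulation of Cox's F with no true difference.** Set-up A used log-normal frailty, four-weekly detection, treatment of 60 to 128 weeks and 1,000 trials per scenario. Set-up B used gamma frailty, a common 24-month horizon and 4,000 trials per scenario. Entries are the percentage of trials rejecting at a nominal 5%; column headings give the proportion of brackets failing.

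| Clustering (frailty variance; log scale in A) | A, 10% | B, 5% | B, 10% | B, 20% |
|---|---|---|---|---|
| None | 5.9 | 6.1 | 5.2 | 5.0 |
| Patient 2 | 2.5 | 5.2 | 3.8 | 2.1 |
| Side 1 | 11.6 | 8.0 | 10.0 | 13.4 |
| Side 2 | 14.0 | 10.7 | 13.8 | 18.1 |
| Patient 1 and side 1 | 12.6 | 9.0 | 10.8 | 12.3 |

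At 5% failures, set-up A gave 8.5% and 11.8% for side variance 1 and 2. At 3% failures (about 9 events), set-up B gave 4.4% to 7.3%, but in 1.8% to 4.5% of trials one adhesive had no failure and F could not be computed. The Monte Carlo standard error in B is about 0.3 percentage points near 5% and 0.6 near 18%.

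**Alternatives on simulated data.**

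- One score per patient (set-up A): 3.3% to 5.4%.
- Log-rank score with patient-clustered variance (set-up B): 3.4% to 5.1%.
- A further simulation at 5% to 10% failures: 4.0% to 5.3% for a permutation swapping sides within patients and 3.7% to 4.9% for the patient-clustered score test. Cox's F ranged from 3.0% (patient effects only) to 10% to 18% (side variance 1 to 2).
- Stratifying the log-rank test by patient does not remove the side effect: 8.0% to 16.7%.

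**What a bare p-value hides.** If 5% of 300 brackets fail, there are 15 events. Treating them as independent, for illustration only, the 95% interval for the hazard ratio extends by a factor of exp(1.96 × 2/√15) = exp(1.012) = 2.75 each way. On the same basis, power for a true hazard ratio of 2 is 18%, 27% and 48% with 9, 15 and 30 events.

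**The case against.** The strongest reply is that the distortion may be modest. Diet, oral care and clinician act on both sides of a mouth, so patient effects may dominate. A simulation with patient log-frailty variance 1 to 2 and side variance only 0.1 to 0.25 gave Cox's F an error rate of 4.7% to 6.1% at 10% failures, 5.5% to 6.7% at 5% and 4.4% to 5.0% at 3%. Side variance 0.5 gave 8.0% to 8.3%, 7.4% to 7.6% and 5.3% to 6.3%. The largest figures need a wide spread between sides: log-frailty variance 1 means a hazard ratio of about exp(2 × 1.96) = 50 across the middle 95% of sides. Nothing in the documents supports or excludes that. The two effects can also cancel exactly, as the third row of the analytic table shows.

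This stands as a limit on the size of the error. It does not rescue the test, because the plan gives no ground for assuming the favourable case.

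Three smaller points also stand. The factor of 2.75 rests on independence. A change of test does not cure the shortage of events. A hazard ratio cannot be estimated if one adhesive has no failures, so the replacement needs a rule for that. Finally, the plan never says that it will read a non-significant result as equal survival; the wording suggested on this is a safeguard.

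**Conclusion.** The concern holds. A test for two independent samples is prescribed for paired, clustered data, so its reference distribution is wrong for this design. The direction of the error is unknown in advance. Under assumed failure rates of 5% to 20%, the simulated false-positive rate ran from 2.1% with strong patient effects to 18.1% with strong side effects. It is close to nominal when patient effects dominate or when only about 3% of brackets fail. The patient-level methods stayed between 3.3% and 5.4% in the scenarios where they were simulated.

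That the method is invalid, and that no effect estimate is planned, follow from the documents alone. The size depends on failure rates and correlations that they do not give. The missing hazard ratio and interval would be a defect even if brackets were independent.

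**What to change.** Replace the Cox's F sentence with wording such as:

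> Time to first failure of each bracket will be analysed with a Cox model with adhesive as covariate and a sandwich variance clustered on patient. The hazard ratio will be reported with its 95% confidence interval. The p-value will come from a permutation of the log-rank score that swaps the two sides within each patient, as in the randomisation. A non-significant result will not be interpreted as equal survival.

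Two additions would close gaps. State that the permutation p-value decides significance if it and the interval disagree near 0.05. State also that, if one adhesive has no failures, the hazard ratio will be reported as not estimable, with failure counts by adhesive and the permutation p-value given instead. A patient-stratified log-rank test is not an adequate substitute.

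The cost is analysis wording and a few lines of code, with no new patients, data or procedures. The interval will be wider than one that assumes independence if failures cluster by side, and narrower if shared patient effects dominate.

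### Cox's F, the only planned test of bracket survival, is undefined in its usual form if one adhesive has no counted failures, and the plan names no fallback

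*Combined protocol and SAP*

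**What the plan says.** Bond survival is the second of the four listed purposes and the second anticipated outcome. The Statistical analysis section assigns it one test: "Bracket survival times will be compared using a Cox's *F* test". No formula, version, software or zero-failure rule is given. The other tests do not fill the gap. The t-test and Mann-Whitney rule is for uncensored group differences, and Cochran-Armitage is reserved for the adhesive remnant index. The threshold is general: "For all tests, *P*-values of less than 0.05 will be considered statistically significant". Sidedness is not stated.

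Three features of the Methods bear on the number of failures:
- Sample: "Thirty consecutive patients presenting for comprehensive orthodontic treatment with fixed appliances".
- Teeth: "The patients will have their maxillary incisors, canines, and premolars bonded with ceramic orthodontic brackets", with one adhesive on each side.
- Counting rule, under Bond survival: "Bond failure as a consequence of habits and trauma will be excluded from the evaluation".

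On allocation, the Methods state: "The side allocation and order of bonding will be randomized for each patient".

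**The concern.** A test that needs at least one failure on each side can fall silent when all the failures are on one side. It would report a P-value for 1 against 8 failures and none for 0 against 8, although the second split is the more one-sided. The sample is small and some failures are not counted, so an adhesive with no counted failures cannot be ruled out.

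If that happened, the test would have to be chosen after the data were seen, and the choice can decide significance. For 0 against 4 failures among 150 brackets each, treated as independent, a log-rank test gives P = 0.044 and Fisher's exact test gives P = 0.12.

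**Working it through.** The plan gives no failure rate, event count or power figure, so there is nothing of its own to reproduce.

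**Inputs.** From the Methods: 30 patients; 2 incisors + 1 canine + 2 premolars = 5 brackets per side; 30 × 5 = 150 brackets per adhesive if no teeth are missing. Assumed: cumulative failure rates per bracket of 1% to 6%, independent brackets unless stated, and two-sided tests.

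**Step 1: is the statistic defined?** With S the summed exponential scores and r the failures in each group, F = (S1/r1)/(S2/r2), referred to F(2r1, 2r2). Illustrative failure times and a common end of follow-up were used.
- 1 v 8 failures: F = (5.073/1)/(4.927/8) = 8.24 on 2 and 16 degrees of freedom, P = 0.007.
- 0 v 8 failures: the first term is 4.561/0 and the reference is F(0, 16). There is no statistic and no P-value.
- 0 v 3, 4, 5, 6 and 10, and 0 v 0, fail in the same way.

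**Step 2: how often is an adhesive free of failures?** For one adhesive, P0 = (1 − p)^150. For at least one of two with equal rates, 1 − (1 − P0)².

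| Rate p | P0 | At least one adhesive with none |
|---|---|---|
| 1% | 0.2215 | 39% |
| 2% | 0.0483 | 9% |
| 3% | 0.0104 | 2% |
| 5% | 0.0005 | 0.1% |

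Clustering within patient raises these chances. With a within-patient correlation of 0.1 (beta-binomial), P0 becomes 0.2855, 0.0806, 0.0225 and 0.0017.

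**Step 3: how often is a clear result lost?** Take 0 v 6 or more as clear. The exact binomial two-sided P is 2 × 0.5^6 = 0.031 for 0 v 6, but 2 × 0.5^5 = 0.0625 for 0 v 5. The chance is P0 of one adhesive times P(X ≥ 6) of the other, summed over both directions.

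| True rates | Main term | Chance of 0 v 6 or more |
|---|---|---|
| 1% v 1% | 2 × 0.2215 × 0.0042 | 0.2% |
| 2% v 2% | 2 × 0.0483 × 0.0819 | 0.8% |
| 3% v 3% | 2 × 0.0104 × 0.2957 | 0.6% |
| 5% v 5% | 2 × 0.0005 × 0.7656 | 0.07% |
| 3% v 6% | 0.0104 × 0.8917 | 0.9% |
| 2% v 4% | 0.0483 × 0.5576 | 2.7% |
| 2% v 6% | 0.0483 × 0.8917 | 4.3% |
| 1% v 3% | 0.2215 × 0.2957 | 6.6% |
| 1% v 6% | 0.2215 × 0.8917 | about 20% |

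**Step 4: would other tests answer?** For 0 v 6 with brackets treated as independent, the two-sided P-values are: log-rank (the score test of a Cox model) 0.014; Cox likelihood-ratio 0.004; Fisher 0.030; exact binomial 0.031.

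**Step 5: what does a within-patient swap test need?** If k patients have unequal sides, the smallest two-sided P is 2/2^k: 0.25 for k = 3, 0.0625 for k = 5 and 0.031 for k = 6. At least 6 such patients are needed. In simulation at 1% v 6% with correlation 0.1, 21.6% of trials had 0 v 6 or more brackets, but 17.0% had a zero side and at least 6 affected patients. At correlation 0.2 the figures were 22.8% and 13.9%.

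**The case against.** The strongest reply is that the harm depends on rates the documents do not give. Follow-up runs to the end of orthodontic treatment, and nothing in the text supports a cumulative rate near 1%. At about 3% or more on both sides the problem nearly vanishes. The failure counts would be visible in any report, and this is described as an initial study with four purposes. All of that stands and limits the weight of the point. It does not supply the missing rule.

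Four stronger readings are tempting, and the documents do not support them.
- **That Cox's F can never be computed at a zero count.** A half-event-corrected version with 2r + 1 degrees of freedom can be (0 v 6: P = 0.006). The plan does not say which version it means, so naming that one would itself be a repair.
- **That up to 39% of trials would lose a finding.** That figure assumes equal rates, where there is no difference to find. It includes 0 v 0 (0.2215² = 4.9% at 1%) and many splits too small to count as clear.
- **That Cox regression would fail for the same reason.** With no failures on one side, only the hazard-ratio estimate and its Wald test break down. The score and likelihood-ratio tests remain defined, as Step 4 shows.
- **That a split such as 0 v 9 is the strongest evidence the trial could give.** Larger splits are stronger: the exact binomial P is 0.004 for 0 v 9 and 0.002 for 0 v 10.

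**Conclusion.** The point holds as a contingent gap. The only named survival test, in its usual form, has no value when one adhesive has no counted failures, and the plan states neither a corrected version nor an alternative. It matters only if one adhesive's cumulative failure rate is about 2% or less. Even then, the chance of losing a clear result ranges from under 1% at equal rates to about 20% at 1% v 6%, a sixfold ratio chosen for illustration.

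These sizes rest on assumed rates, 150 brackets per adhesive and independent brackets. The P-values in Steps 1 and 4 also treat brackets as independent. Clustering makes a zero count more likely, but it also makes a given one-sided split less convincing. The failure of the plan to allow for clustering is a separate matter; the zero-count problem would exist without it.

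**What to change.** In the Statistical analysis section, replace Cox's F with a log-rank score test (observed minus expected failures on the flash-free side). Build its reference distribution by swapping the two adhesive labels within each patient. This is defined at a zero count and follows the side randomisation already planned. It also copes with the ties to be expected when "Possible bond failure will be recorded at standardized intervals of four weeks". State that the test is two-sided. Report the failure percentage for each adhesive and the difference between them, with an interval that exists at a zero count and allows for clustering within patient.

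The cost is revised wording and a few lines of code, with no new data. The drawback is a coarse P-value: fewer than 6 patients with unequal sides cannot reach two-sided P < 0.05, so 0 v 6 brackets concentrated in three patients would give P = 0.25 at best. A plain log-rank test, or a one-line fallback, would also cure the zero-count problem, but would still treat brackets as independent.

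### The Cochran-Armitage test for the adhesive remnant index treats scores from the same mouth as independent, so its 5% level is not assured in either direction

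*Combined protocol and SAP*

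**What the plan says.** The design is split-mouth. Under Methods, "The patients will have their maxillary incisors, canines, and premolars bonded with ceramic orthodontic brackets", with a different adhesive on each side, and "The side allocation and order of bonding will be randomized for each patient". The Bonding time section makes the two groups the two sides of one mouth: the flash-free "product on one side (group 1) and the conventional (APC II) product on the other side (group 2").

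ARI is recorded at the end of treatment (Adhesive remnant cleanup): "Once the brackets are debonded, the adhesive remnant index" is scored under magnification. The section does not say whether the unit of analysis is the bracket, the side or the patient.

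The Statistical analysis section then states: "A Cochran-Armitage test will be used to determine if there is an association between group membership and ARI". It adds: "For all tests, *P*-values of less than 0.05 will be considered statistically significant". It mentions no pairing, clustering, stratified or permutation version of the test, or side-level summary for ARI. The sample is 30 patients, without a sample-size calculation.

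**The concern.** The Cochran-Armitage test takes its variance from a table of independent observations. Here both columns of the table come from the same 30 people, and each person probably contributes several scores to each column. Two kinds of correlation then act in opposite directions:

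- **Correlation shared by the whole mouth** cancels in the comparison of sides. The test does not know this, so its variance is too large. It becomes conservative and can miss a real difference.
- **Correlation specific to one side** does not cancel. Treating five teeth on a side as five independent results makes the variance too small, and false positives rise.

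ARI is the only measure for the third stated purpose, the amount of adhesive left on the tooth. If the variance is wrong in an unknown direction, neither a significant nor a null ARI result can be read at face value. The test also gives up the main statistical advantage of a split-mouth design, the removal of differences between patients.

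**Working it through.** The plan gives no power, ARI distribution or correlation, so there is no figure of its own to reproduce. The check asks what the true size of the planned test is.

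**Inputs from the document.** 30 patients; both adhesives in each patient, with side randomised; level 0.05 (two-sided assumed). Teeth per side: 2 incisors + 1 canine + 2 premolars = 5, hence 30 × 5 = 150 scores per adhesive if every bracket is scored.

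**Assumptions.** Analysis by bracket, which is the natural reading but is not stated. Four ARI categories with equal frequencies, since the document gives neither number nor distribution. Correlations from a range, because none is given.

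**Formula.** Let p be the correlation shared by the whole mouth (ICC_patient) and s the additional correlation within a side (ICC_side), both on the score scale. Two teeth on the same side correlate p + s; two teeth on opposite sides correlate p. With five teeth per side,

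variance ratio (true / assumed) = 1 + 4(p + s) − 5p = 1 − p + 4s,

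true size = 2 × [1 − Φ(1.96 / √ratio)].

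The test is liberal when 4s > p, conservative when 4s < p, and close to nominal when they balance.

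**Two worked values.** A latent patient correlation of 0.4 is about 0.35 on the score scale. With s = 0 the ratio is 1 − 0.35 = 0.65; 1.96/√0.65 = 2.43, a true size of about 1.5%. For a latent side correlation of 0.2 alone the ratio is 1.69; 1.96/√1.69 = 1.51, a true size of about 13%.

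**Simulation.** 10,000 trials per setting, 30 patients × 2 sides × 5 teeth, latent normal with patient, side and tooth effects cut at quartiles. Correlations are on the latent scale.

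| Patient | Side | Size of planned test (nominal 5%) |
|---|---|---|
| 0.2 | 0 | 3.3% |
| 0.4 | 0 | 1.8% |
| 0.6 | 0 | 0.5% |
| 0 | 0.1 | 9.3% |
| 0 | 0.2 | 13.4% |
| 0.2 | 0.05 | 4.9% |
| 0.4 | 0.1 | 5.5% |
| 0.4 | 0.05 | 3.4% |
| 0.2 | 0.1 | 7.3% |
| 0.2 | 0.2 | 11.3% |

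Formula and simulated variance ratios agree to within 0.03, for example 0.65 against 0.68 (patient 0.4) and 1.69 against 1.71 (side 0.2). Over the same settings a signed-rank test on side means had size 4.6–5.2%, and a side-swap permutation test 3.5–5.2%. A separate simulation with different code gave 0.9% to 17% for the planned test over its own range of correlations, and 4.6–5.3% for a paired t-test on side means.

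**Power at a latent shift of 0.3, planned against signed-rank.** 71% against 81% (patient 0.4); 73% against 91% (patient 0.6); 67% against 62% (patient 0.4, side 0.1).

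**If ARI is reduced to one score per side (median).** The test still ignores the pairing. Its size is 1.3% and 0.3% at patient correlations of 0.2 and 0.4.

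**The case against.** The strongest reply is that inflation has not been shown. Pairing alone, with positive correlation, makes the test conservative, so false positives stay below 5% and the only harm is lost power. Inflation needs a second condition: brackets entered singly, with side-level clustering large enough that 4s exceeds p. The document does not name the unit, and the largest sizes (9.3% and 13.4%) come from the boundary case of no patient correlation. The range also includes values near 5%. All of this stands, and it is why no direction is claimed here.

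The magnitudes also depend on the ARI distribution. With an assumed split of 85/8/5/2%, the formula gives 9.8% instead of 13.1% (side 0.2), 7.2% instead of 9.1% (side 0.1) and 2.5% instead of 1.5% (patient 0.4). The near-cancelling case (0.4/0.1) moves from 5.2% to 6.0%. Most departures shrink; none disappears.

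Several valid paired methods exist, and a within-patient permutation of the trend statistic would stay closest to the planned test. None of those discussed here deals with a clinician-by-adhesive effect among the ten clinicians, which is a separate question. The unpaired t and Mann-Whitney tests planned elsewhere in the Statistical analysis section overlook the same pairing.

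No reading of the plan makes the test fit the design. By bracket it ignores clustering and pairing; by side it still ignores pairing.

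**Conclusion.** The concern holds. The planned ARI test does not match the split-mouth design, and following the plan exactly gives a p-value from the wrong variance. The mismatch is certain from the text. Its size and direction are not, because they depend on correlations the document does not supply. Under the assumed correlations and four equal categories, the true size by bracket ran from 0.5% to 13.4%, with values near 5% where the two correlations cancel. By side it was below 5%. These figures are illustrative. The point should be fixed before analysis: it affects one of the four stated purposes and the correction is a matter of wording.

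**What to change.** Replace the ARI sentence in the Statistical analysis section with wording such as: *For each patient the mean ARI of each side will be computed, and the within-patient differences between adhesives will be tested with a Wilcoxon signed-rank test.* A side-swap permutation test is an equally suitable choice; one of the two should be named in advance as the source of the p-value. This also settles the unit of analysis. Keep the table of ARI by group as description.

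If an odds ratio with a 95% confidence interval is wanted, a cumulative-logit GEE clustered on patient can be added, with a small-sample variance correction. With 30 clusters the uncorrected version had size 5.8–6.5%; a variance factor of 30/29 with a t reference on 29 degrees of freedom gave 4.3–5.3%.

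The cost is analysis wording only, with no new data. The p-value may be less favourable if scores cluster by side, and where the two correlations cancel the paired test is slightly less powerful (62% against 67% at patient 0.4, side 0.1).
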